6.4 DEMOGRAPHY AND BASELINE VARIABLES

At the Day 0 visit, information is collected on the participant's previous COVID-19 vaccines (including vaccine, dates, and any reactions experienced), history of previous SARS-CoV-2 infections, demographics (e.g. age, sex, ethnicity), comorbidities, and clinical observations before trial vaccination. Details of demography and baseline parameters are stored in RedCAP Codebooks.

6.5 INTERCURRENT EVENTS

Data will be collected throughout the 12-month follow-up period on receipt of COVID-19 vaccines (including date and vaccine) and breakthrough SARS-CoV-2 infections (including date and severity). These will be considered intercurrent events in the analysis; the strategies used for handling these events are detailed in Estimand-to-Analysis tables in Sections 7 and 8. Intercurrent event parameters are detailed below:

Intercurrent event	Potential impact if ignored
Breakthrough SARS-CoV-2 infection	Breakthrough infections will have a boosting effect on immunological markers, making the trial vaccine appear more immunogenic than it truly is. High incidence of breakthrough infections due to reduced immunogenicity in one group could give the appearance of greater immunogenicity of the trial vaccination in this group relative to other groups in which breakthrough infections have been more successfully prevented.
Receipt of 5 th dose (self-initiated)	Receipt of a 5 th dose will have a boosting effect on immunological markers, making the trial vaccine appear more immunogenic than it truly is. Higher uptake of the 5 th dose in one group could give the appearance of greater immunogenicity of the trial vaccination in this group relative to other groups with lower 5 th dose uptake.

Lost-to-follow-up and other events resulting in missing data will be treated as a missing data problem (see Section 4.10 "Handling of missing data".

7 ANALYSIS OF THE PRIMARY OUTCOMES

7.1 PRIMARY ENDPOINTS

7.1.1 Immune response at Day-28

The primary endpoint is binding antibody at the Day 28 visit for Wuhan (BAU/ml) as evaluated using the Euroimmun S1 IgG ELISA, comparing the two vaccine groups (Groups A and B).

7.1.2 Reactogenicity within 7 days of boosting

Reactogenicity will be measured using a standardised daily questionnaire (diary card) that elicits the presence and severity (mild, moderate, severe, life-threatening [grades 1-4, respectively]), or absence, of local reactions (pain, tenderness, redness, hardness, swelling, necrosis, warmth, or itch at or near the injection site) or systemic reactions (fever, nausea, vomiting, diarrhoea, headache, fatigue/malaise, myalgia, arthralgia, or enlarged lymph nodes) within the last 24 hours on days 1 through 7. Warmth and itch will be recorded as presence/absence only (i.e., not graded). The primary endpoint for reactogenicity will be solicited grade 3 or 4 local or systemic reactions within 7 days of vaccination.

Table 5 outlines the primary endpoints, including the timepoint, population summary measure, comparison groups and measure of association.

Table 5. Primary endpoints

Primary Endpoint	Outcome	Timepoint	Population measure	Comparison	Measure of association
i.	Binding antibody for Wuhan	Day-28 visit	Geometric mean concentration (GMC) (95% CI)	Group A vs Group B (Nb. Group A consists of Moderna BA.1 and BA.4-5 combined)	Geometric mean ratio (GMR)
ii.	Reactogenicity: solicited grade 3 or 4 local or systemic reactions within 7 days of vaccination, inclusive	7 days post-booster	% (95% CI)	NA (descriptive)	NA (descriptive)

7.2 MAIN ANALYSIS OF THE PRIMARY ENDPOINTS

Table 6 and Table 7 are the Estimand-to-analysis tables for the primary immunological and reactogenicity endpoints, respectively.

Table 6. Estimand-to-Analysis table⁵ for immune response (binding antibodies- IgG) at Day-28 (primary immunogenicity endpoint)

Primary Objective (as per Protocol):	
Assess and compare the immune response in two randomised vaccine groups (bivalent Moderna and Novavax) at 28 days post-vaccination measured as binding antibodies (IgG ELISA – Wuhan) who have been boosted at least six months earlier.	
Estimand:	Geometric mean ratio (GMR) of binding antibodies (IgG ELISA – Wuhan) 28 days post-vaccination comparing the two vaccine groups (bivalent Moderna and Novavax) in adults 18 years or older who have received their third dose of COVID-19 vaccine at least six months previously, irrespective of SARS-CoV-2 infection.
ESTIMAND Attributes:	Incorporation of Estimand Attribute in ANALYSIS:
Treatment Bivalent mRNA Moderna COVID-19 vaccine and protein-based Novavax COVID-19 vaccine	Study arms Bivalent Moderna vaccine arm (Moderna BA.1 and Moderna BA.4-5 groups combined) Novavax vaccine arm
Target population Adults 18 years or older who have received their third dose of COVID-19 vaccine at least six months previously	Analysis set (“Primary Day-28 Immunology Population”) All randomised participants as per randomisation with complete outcome and covariate data
Variable Binding antibodies (IgG ELISA for Wuhan, Omicron BA.1 and Omicron BA.4/5) 28 days after trial vaccination	Outcome measure Geometric mean concentrations of binding antibodies at the Day-28 visit (25 – 35 days post-booster)
Handling of intercurrent events	Handling of missing data
Event (up to and including Day-28 visit)	Strategy⁴
SARS-CoV-2 infection	Treatment Policy [#] (interpret results in conjunction with breakthrough infection rates) If >5% of participants are excluded due to missing data, a supplementary analysis will be performed with multiple imputation.
Population-level summary measure Geometric mean ratio	Analysis approach Linear regression will be used to estimate the GMR comparing the two vaccine groups, adjusted for the stratifying variable (age group), baseline levels, first booster vaccine and time since first booster. The outcome variable (and the baseline value) will be \log_e transformed before regression, and the GMR (95% CI) will be calculated as the antilogarithms of the mean difference (β_1) and its 95% CI.

[#]Supplementary analyses will be conducted using the Hypothetical Strategy for handling intercurrent events (see Table 14).

Table 7. Estimand-to-Analysis⁵ table for at least one solicited grade 3 or 4 local or systemic reaction within 7 days of boosting (primary reactogenicity endpoint)

Primary Objective (as per Protocol): Assess the rate and severity of reactogenicity within one-week post-second booster for the Moderna and Novavax groups (Timepoint – daily, for seven days post-vaccination).	
Estimand:	Incidence risk of a grade 3 or 4 local or systemic reaction within 7 days (inclusive) of boosting, by vaccine group in adults 18 years or older who have received their third dose of COVID-19 vaccine at least six months previously
ESTIMAND Attributes:	Incorporation of Estimand Attribute in ANALYSIS:
Treatment Bivalent mRNA Moderna COVID-19 vaccine and protein-based Novavax COVID-19 vaccine	Study arms Bivalent Moderna vaccine arm (Moderna BA.1 and Moderna BA.4-5 groups combined) Novavax vaccine arm
Target population Adults 18 years or older who have received their third dose of COVID-19 vaccine at least six months previously	Analysis set (“Reactogenicity Population”) All participants, as per trial vaccine received (regardless of allocation).
Variable Grade 3 or 4 local or systemic reaction within 7 days (inclusive) of boosting.	Outcome measure Presence of at least one solicited grade 3 or 4 local or systemic reaction within 7 days (inclusive) of boosting.
Handling of intercurrent events	
Event (up to and including Day-7)	Strategy⁴
SARS-CoV-2 infection	While Negative (values up to the day of the first positive test are used)
Death	While Alive (values up to the time of death are used)
Population-level summary measure Incidence risk (proportion) of at least one solicited grade 3 or 4 local or systemic reaction within 7 days (inclusive) of boosting.	Handling of missing data It will be assumed that participants with missing reactogenicity datapoints (collected daily for each reaction type) did not experience the specific reaction on the day/s where the value is missing. Missing data by day and reaction will be described by study group. Analysis approach Proportions will be estimated with 95% Clopper-Pearson binomial confidence intervals using the ci Stata command. Supplementary analysis: The following reaction-specific descriptive analyses will also be conducted: 
Number and percentage of individuals with each reaction type, presented in a radial graph (Dummy Figure 2).Number and percentage of participants with each reaction type, by severity grade (Dummy Figure S 1).Distribution of the day of onset for each reaction typeDistribution of the duration of each reaction type

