	
  
 Group	Vaccine given	
   
 Group A – (Moderna) 225 participants	Bivalent Moderna (mRNA-1273.214) (Ancestral SARS-CoV-2 25µg + Omicron Variant (B.1.1.529) 25µg). Replaced by Bivalent Moderna (mRNA-1273.222) (Ancestral SARS-CoV-2 25µg + Omicron Variant (BA.4-5) 25µg) when introduced.	
 
 Group B – (Novavax) 225 participants	Novavax (5µg of SARS-CoV-2 spike protein adjuvanted with 50µg of Matrix-M)	
 
 **Group C – (Control group) 150 participants	No vaccine given	
  
		Group	Vaccine given	Group A – (Moderna) 225 participants	Bivalent Moderna (mRNA-1273.214) (Ancestral SARS-CoV-2 25µg + Omicron Variant (B.1.1.529) 25µg). Replaced by Bivalent Moderna (mRNA-1273.222) (Ancestral SARS-CoV-2 25µg + Omicron Variant (BA.4-5) 25µg) when introduced.	Group B – (Novavax) 225 participants	Novavax (5µg of SARS-CoV-2 spike protein adjuvanted with 50µg of Matrix-M)	**Group C – (Control group) 150 participants	No vaccine given
Group	Vaccine given									
Group A – (Moderna) 225 participants	Bivalent Moderna (mRNA-1273.214) (Ancestral SARS-CoV-2 25µg + Omicron Variant (B.1.1.529) 25µg). Replaced by Bivalent Moderna (mRNA-1273.222) (Ancestral SARS-CoV-2 25µg + Omicron Variant (BA.4-5) 25µg) when introduced.									
Group B – (Novavax) 225 participants	Novavax (5µg of SARS-CoV-2 spike protein adjuvanted with 50µg of Matrix-M)									
**Group C – (Control group) 150 participants	No vaccine given									
	
*Participants and reactogenicity assessors will be blinded for seven days as vaccine details will be uploaded to the Australian Immunisation Register seven days post-vaccination.
 
**Control group will not be randomised and will be recruited into proportional predefined age bands (18-29 years, 30-49 years, 50-59 years).
									
JUSTIFICATION	
 Investigating a fourth dose will allow us to explore whether additional boosters are needed in a setting with high rates of prior infection. We will include a non-randomised control group aged under 60 years who will not receive a fourth dose to investigate whether three doses are adequate for this age group and what additional benefit a fourth dose provides in terms of cellular immunity as a proxy for moderate/severe disease. 									

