3.2.3 Exploratory outcomes

- At baseline, previous infections (RAT or PCR positive or symptomatic with close contact) and vaccinations will be recorded.
- Breakthrough infections will be recorded and tested for during the study.
- Nasal swabs will be collected from all severe breakthrough cases and a subset of mild cases within three days of illness. A representative sample of positive samples will be processed for viral load and whole genome sequencing of SARS-CoV-2.
- We will explore the differences in viral load and viral genome characteristics and immunological markers among mild and severe breakthrough cases.

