11.3.2. Secondary outcomes

Binding antibodies - changes from baseline will be expressed as geometric mean fold ratios (GMFR), calculated as the ratio of the post-booster GMC to the baseline GMC. GMCs will be compared between the two vaccine groups and between the vaccine and control groups at 6, 12, 18, 24 and 30 months. We will account for age in the analysis.

Functional antibodies seven time points for vaccine groups [baseline, 1, 6, 12, 18, 24 and 30 months] and six time points for controls [baseline, 6, 12, 18, 24 and 30 months] – for the C-PASS assay (sVNT), data are reported as percentage (%) inhibition by neutralising antibodies using the manufacturer’s instructions. A <30% inhibition is considered negative, while ≥30% inhibition is considered positive. Data will be presented as mean and standard deviation.

Neutralizing assay (20% subset of samples at all time points) up to 12 months – Data will be reported as endpoint titre calculated using the Reed/Muench method (23). A titre of 10 reflects undetectable neutralizing activity.

Cellular immunity: (on a 50% subset at seven time points for vaccine groups and six time points for controls)

Quantiferon COVID IFNy release assay up to 12 months – Levels of IFNy will be reported in IU/ml according to the manufacturer’s instructions. Data will be reported as GMT and 95% confidence intervals.

IFNy Elispot – The number of IFNy-producing cells/million PBMCs will be reported using means and 95% confidence intervals.

Intracellular cytokine staining – The data will be reported as the frequency (%) of cytokine-expressing T cells (e.g., total T cells, CD4 T cells, CD8 T cells). Cytokines such as IFNy (Th1) and IL-5 (Th2) will be measured as a minimum. This will be presented as means and 95% confidence intervals.

Multiplex cytokine assays – A 10-plex panel of cytokines will be measured in supernatants from the Elispot studies. Cytokine concentrations will be reported in pg/ml, and data will be presented as GMT and 95% confidence intervals.

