1.3 SUMMARY OF CHANGES COMPARED TO THE PROTOCOL

- The primary objective as worded in the protocol is to *“Assess and compare the immune response in two randomised vaccine groups (bivalent Moderna and Novavax) at 28 days post-vaccination measured as binding antibodies (IgG ELISA – Wuhan and/or Omicron) who have been boosted at least six months earlier.”* In this SAP, binding antibodies for Wuhan will be treated as the primary outcome, with other (sub)variants (e.g. Omicron BA.1 and Omicron BA.4/5) treated as secondary outcomes.
- The protocol specified that binding IgG data using the Euroimmun S1 IgG ELISA kits will be reported as relative units/ml (RU/ml) per the manufacturer’s instructions, with the units converted to BAU/ml for Wuhan. Whereas they will remain RU/ml for Omicron BA.1. For the Omicron BA.4/5 binding IgG data, an in-house ELISA will be used, the units are EU/ml.
- The protocol specified two different sets of adjustment variables to be included in the linear regression model for the primary analysis of the primary immunogenicity endpoint (IgG at Day-28). In this SAP, the adjustment variables have been updated to be: age group, baseline levels, first booster vaccine and time since the first booster.

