	
first booster vaccine, time since first booster vaccine and baseline [OUTCOME]* levels.
 
Where the population-level summary measure is the GMR, the outcome variable (and the baseline value) will be \log_e transformed prior to regression, and the GMR (95% CI) will be calculated as the antilogarithms of the mean difference (β_1) and its 95% CI.
 
When zero and negative values are expected, the population-level summary measure will be the difference in medians. This will be estimated using quantile regression with the same adjustment variables as above.
 
Planned figures The distribution of the immunological data will be displayed using a scatterplot overlaid with median and interquartile range (see Dummy Figure 3)

--	---

This table is generic for all secondary Day-28 immunological endpoints (see **Table 8, which will be analysed in the same way depending on their distributions; the population measure for outcomes with skewed distributions is the geometric mean and the population-level summary measure of association is the GMR – baseline and Day-28 values will be \log_e transformed prior to analysis*

Table 10. Generic Estimand-to-Analysis table for all secondary Month-6, Month-12, Month-18 and Month-24 immunological endpoints (specified in Table 8).

Primary Objective (as per Protocol): Compare the immunogenicity in two randomised vaccine groups (bivalent Moderna and Novavax) at 6, 12, 18, 24, 30 months post-vaccination.	
Estimand:	[MoA]* of [OUTCOME]* 6/12/18/24/30 months post-vaccination comparing the two vaccine groups (bivalent Moderna and Novavax) in adults 18 years or older who have received their third dose of COVID-19 vaccine at least six months previously, irrespective of SARS-CoV-2 infection or receipt of a 5 th dose (self-initiated).
ESTIMAND Attributes:	Incorporation of Estimand Attribute in ANALYSIS:
Treatment Bivalent mRNA Moderna COVID-19 vaccine and protein-based Novavax COVID-19 vaccine	Study arms Bivalent Moderna vaccine arm Novavax vaccine arm
Target population Adults 18 years or older who have received their third dose of COVID-19 vaccine at least six months previously	Analysis set (“Month-6/12 Immunology Population”) All randomised participants as per randomisation with complete outcome and covariate data
Variable [OUTCOME]*, 6/12 months after boosting.	Outcome measure [OUTCOME]* at the Month-6/12 visit (6/12 months +/- 14 days post-booster).

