Handling of intercurrent events	Handling of missing data The proportion of participants excluded due to missing outcome or covariate data will be described by study group. If >5% of participants are excluded due to missing data, a supplementary analysis will be performed with multiple imputation.
Population-level summary measure Geometric mean ratio (GMR) OR Difference in Means*	Analysis approach Linear regression will be used to estimate the difference in mean [OUTCOME]* between the vaccine arms, adjusted for the stratifying variable (age group), primary series and first booster vaccine, and baseline [OUTCOME]* levels. Where the population-level summary measure is the GMR, the outcome variable (and the baseline value) will be log_e transformed before regression, and the GMR (95% CI) will be calculated as the antilogarithms of the mean difference (β_1) and its 95% CI. When zero and negative values are expected, the population-level summary measure will be the difference in medians. This will be estimated using quantile regression with the same adjustment variables as above. The distribution of the immunological data at each timepoint will be displayed using a scatterplot

	overlaid with median and interquartile range (see Dummy Figure 3)
--	---

*This table is generic for all secondary Month-6 and Month-12 immunological endpoints (see Table 8), which will be analysed in the same way depending on their distributions; the population measure for outcomes with skewed distributions is the geometric mean and the population-level summary measure of association (MoA) is the GMR – baseline and Month-[6/12] values will be log_e transformed before analysis; the population measure for normally distributed outcomes is the mean and the population-level summary measure of association (MoA) is the Difference in Means. For outcomes with skewed distributions and negative values, the population summary measure of association is the difference in medians, which will be estimated using quantile regression.

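### Prior infection, recorded at Day 0, is in none of the immunogenicity models, and the Month-6+ model also omits time since first booster, so a small gain in precision is forgone

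*SAP*

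**What the plan says.** **Models.** The three estimand-to-analysis tables for immunogenicity list these covariates:

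- SAP 7.2, Table 6 (primary, Day 28): "adjusted for the stratifying variable (age group), baseline levels, first booster vaccine and time since first booster".
- SAP 8.1.1, Table 9 (secondary, Day 28): age group, "first booster vaccine, time since first booster vaccine and baseline [OUTCOME]* levels".
- SAP 8.1.1, Table 10 (Month 6 onward): age group, "primary series and first booster vaccine, and baseline [OUTCOME]* levels".

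SAP 1.3 explains only the Day-28 primary set: "the adjustment variables have been updated to be: age group, baseline levels, first booster vaccine and time since the first booster". For the later visits, Protocol 11.3.2 says of binding antibody "We will account for age in the analysis".

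**Data.** Protocol 3.2.3 states "At baseline, previous infections (RAT or PCR positive or symptomatic with close contact) and vaccinations will be recorded". SAP 6.4 lists "history of previous SARS-CoV-2 infections" among the Day-0 variables. SAP 4.9 requires the dates of the first three doses to be locked before any immunological endpoint is analysed. SAP Table 3 lists N-protein IgG for all participants, but its only stated use is to define undocumented breakthrough infection (SAP 9.1).

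**Subgroups.** SAP 9.5 plans subgroups by age stratum and by Moderna product period. It plans none by prior infection, and Dummy Table 1 has no row for it.

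**Rationale.** The protocol synopsis justifies the trial partly as a way to "explore whether additional boosters are needed in a setting with high rates of prior infection".

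**The concern.** A baseline variable that predicts antibody level can narrow the confidence interval of a randomised comparison at almost no cost. Prior infection is a natural candidate: the protocol expects it to be common, and eligibility excludes only confirmed infection in the last three months. Baseline antibody level is adjusted for, but it does not separate a response left by infection from one left by the third dose.

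The covariate set also changes between Day 28 and Month 6 without explanation. Time since first booster is dropped and primary series added, although the dates needed for the former are required for every endpoint. What is at stake is some precision in the geometric mean ratio (GMR), and a planned look at whether the vaccine comparison varies with prior infection.

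**Working it through.** **1. Reproduce the plan's sample size (SAP 3.5).** Inputs: CV 1.15, GMR 1.4, two-sided 0.05, power 90%.

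- Log SD = √ln(1 + 1.15²) = 0.918; ln 1.4 = 0.336.
- n per arm = 2 × (1.960 + 1.282)² × 0.918² / 0.336² ≈ 157 (158 with the t distribution). The plan's 160 is reproduced.
- 160 / 0.80 = 200, as stated. The final 225 per arm less 20% leaves 180 evaluable.

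This calculation uses the unadjusted SD, so the sample size does not depend on the missing covariates.

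**2. Gain from the added terms.** Let r be the share of residual variance that the added terms explain beyond the existing covariates, including baseline titre. The documents give no value for r; 0 to 0.10 is an assumption.

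- Interval narrowing on the log scale = 1 − √(1 − r).
- Equivalent extra participants = 1/(1 − r) − 1.
- Power at 180 per arm uses SD = 0.918 × √(1 − r), with no credit for baseline adjustment.

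| r | Interval narrower by | Equivalent extra n (per arm at 180) | 95% CI factor at 180 | Power for GMR 1.4 |
|---|---|---|---|---|
| 0 | 0% | 0 | 1.209 | 93.5% |
| 0.02 | 1.0% | 2.0% (about 4) | 1.207 | 94.0% |
| 0.05 | 2.5% | 5.3% (about 9) | 1.203 | 94.6% |
| 0.10 | 5.1% | 11.1% (20) | 1.197 | 95.6% |

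If the existing covariates already explain an assumed 30% of variance, power at 180 is 98.6% without the added terms and 99.2% at r = 0.10.

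**3. Cost of the added terms.** Assume 360 observations and about seven parameters already in the model. One more term widens the interval by √(353/352) = 1.0014, or about 0.1%. Two more give √(353/351) = 1.003, or about 0.3%.

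**4. What a subgroup by prior infection could show.** With 180 per arm and a previously infected fraction p (assumed 50% to 80%), the interaction SE is SD × √[2/(180p) + 2/(180(1 − p))].

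- At p = 0.5: SE = 0.918 × 0.211 = 0.194. The ratio of GMRs detectable at 80% power is exp(2.80 × 0.194) = 1.72.
- At p = 0.8 the detectable ratio is 1.97.
- If covariates explain an assumed 50% of variance, the figures are 1.47 and 1.61.

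All of these exceed the trial's own important difference of 1.4.

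**The case against.** **The baseline titre may already carry the signal.** The third dose was at least six months earlier, so very recent vaccination is excluded by design. Tables 6 and 9 also adjust for first booster vaccine and time since it. What remains in the baseline titre plausibly reflects much of the infection history. This stands: r may be close to zero.

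**Table 10 is not arbitrary.** Its set matches one of the two Day-28 sets in Protocol 11.3.1, and it goes beyond the age-only adjustment in Protocol 11.3.2. This also stands. The omission of time since first booster is relative to the Day-28 models, and what is missing is a reason.

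**The change has costs.** The analysis sets require complete covariate data, so a new covariate could remove participants. No N-protein positivity cut-off is given. The extracted Table 3 has a footnote about Day-0 measurement that is not visibly tied to a row. Recorded history includes unconfirmed symptomatic contacts. SAP 1.2 says an earlier SAP covered Day 28, so changing the primary model could now be post hoc; the documents do not say whether that analysis has been run. These points shape the fix but do not remove the concern.

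**A reader might infer that the trial leaves one of its stated questions unanswered.** The documents do not support that. Prior infection appears in the synopsis justification and in Protocol 2.2, but no objective in Protocol 3.1 or SAP 2 asks whether the vaccine comparison differs by infection status. A main-effect covariate would not answer that question anyway.

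**Conclusion.** The omissions are real and the improvement is minor. Under the assumed r of 0 to 0.10, the forgone gain is an interval 0% to 5% narrower, or at most about two points of power on a comparison already above 90%. No main conclusion is likely to turn on it.

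A reader might infer that leaving out prior infection distorts the GMR. For Moderna versus Novavax it does not, because allocation is randomised. A chance imbalance can be worked out. At an assumed 50% prevalence, two SDs is 2 × √(2 × 0.5 × 0.5/180) = 0.105. With an assumed infection effect of 1.2- to 2.0-fold, the GMR would move by 1.2^0.105 = 1.02 to 2.0^0.105 = 1.08. That is ordinary sampling variation which the confidence interval already covers, not a second harm on top of the lost precision.

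Comparisons with the non-randomised control group are a separate matter, since Table 10 names only the two vaccine arms. This point does not rest on them.

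**What to change.** - **Table 10:** add documented prior infection at baseline (yes/no) and time since first booster. State beforehand whether unconfirmed symptomatic contacts count as infection.
- **Tables 6 and 9:** if Day-28 data have already been analysed unblinded, add prior infection as a sensitivity analysis and leave the main model alone. Otherwise add it as a covariate.
- **SAP 9.5:** list prior infection as an exploratory subgroup with an arm-by-infection interaction, and say that it is weakly powered.
- **N-protein IgG:** use it for baseline infection status only if Day-0 values are confirmed to exist and a cut-off is fixed before analysis.
- **SAP 4.9 and Dummy Table 1:** name baseline infection history explicitly in both.

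The cost is SAP wording, one or two more model terms, and possibly a few participants lost to missing covariate data. No new data collection is needed.
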